Mitral Valve Surgery + Tricuspid Valve Annuloplasty

Mitral Valve Surgery Alone

DEFINITIONS AND MEASUREMENT OF ENDPOINTS

Primary Endpoint

The primary outcome of this trial is treatment failure defined as the composite of (1) death from any cause, (2) reoperation for TR, (3) presence of severe TR at two years post randomization or, for patients enrolled with less than moderate TR and annular dilatation, progression by two grades (i.e., from none/trace TR to moderate TR) at two years post randomization.

Secondary Endpoints

Clinical and Functional Outcomes

MACCE (Major Adverse Cardiac and Cerebrovascular Events)

MACCE is defined as a non-weighted composite score comprised of the following components:

- Death
- Stroke
- Serious heart failure events

NYHA Classification and Diuretic Use

Functional status will be assessed by the NYHA Classification scale. Complete NYHA classification guidelines can be found in [Appendix III](#). The diuretic requirements of patients will be assessed.

Six Minute Walk Test (6MWT)

The total distance walked in six minutes will be assessed. Complete 6MWT guidelines can be found in [Appendix IV](#).

Gait Speed Test for Frailty

Frailty will be assessed using the Gait Speed Test administered at baseline and reassessed at 12 and 24 months post-randomization. Complete Gait Speed Test guidelines can be found in [Appendix V](#).

Physiologic

Echocardiographic Parameters (Appendix I and Appendix II)

- Degree of TR at Index Hospital Discharge
- Degree of TR at 12 and 24 months
- RV Size at 12 and 24 months
- RV Function (normal, mildly impaired, moderately impaired, severely impaired, peak tricuspid annular velocity, TAPSE, RVFAC) at 12 and 24 months
- Pulmonary Artery Pressure at 12 and 24 months
- RV volume at 12 and 24 months as measured by transthoracic 3D echocardiography

Quality of Life

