Prior to screening data collection and protocol defined procedures

The patient must sign the Release of Medical Information form or equivalent that authorizes release of medical records, including hospital costing data, to the study sponsors, investigators and monitors.

Demographics Form

At initiation of screening

A screened patient is defined as a consented subject who was referred to, or identified at a clinical site for consideration of entry into the study, and for whom some preliminary (i.e., medical record) data have been collected and/or reviewed. For all patients screened, date of birth, ethnic origin, and sex will be captured on the registration form. The EDC will generate a unique 5-digit identification code that will identify the patient throughout the course of the study.

Echocardiogram

Within 60 days prior to randomization

A complete TTE will be performed according to the specifications defined in the Echocardiographic Image Acquisition Protocol ([Appendix I](#) and [Appendix II](#)) within 60 days prior to randomization. ***The pre-randomization 2D echo will be read by the clinical site echocardiography investigator to assess the degree of TR which will determine echocardiographic eligibility for participation in the trial.*** (See Echocardiography Qualification above) After this initial assessment, the study echo will be sent to the Echocardiography Core Lab for centralized reading. The site echocardiography lab must be accredited by the Echo Core Lab in advance of performing any study echocardiograms. In addition, the sites will perform a 3D TTE to assess RV volume.

Medical History

Within 60 days prior to randomization

This form captures the information pertaining to the medical history, including but not limited to previous myocardial infarction, myocardial revascularization, arrhythmias, AICD, permanent RV or biventricular pacemaker, stroke and other comorbidities such as diabetes and peripheral vascular disease.

Six Minute Walk Test

Within 60 days of randomization

This form captures the distance in feet walked on a level hallway in six minutes (See [Appendix IV](#)). A research clinician trained on the protocol and designated by the PI will oversee the 6MWT. This assessment is repeated at various protocol-defined periods during the trial.

Gait Speed Test for Frailty

Within 60 days prior to randomization

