Six Minute Walk and Gait Speed Tests: Differences between groups in gait speed and the distances travelled during the 6MWT will be compared using the Wilcoxon Rank-Sum test. We will also assess the extent to which changes over time (in gait speed and distance walked) are related to other outcomes.

Additional echo parameters: RV function (normal, mildly impaired, moderately impaired, severely impaired, peak tricuspid annular velocity, TAPSE, RVFAC) at 12 and 24 months and pulmonary artery pressure at 12 and 24 months will be compared between groups. RV volume as assessed by 3D TTE at 12 and 24 months will be compared between groups. Continuous variables will be compared for between group differences using the Wilcoxon Rank Sum test, and the level of function by chi-squared test.

Quality of life: QOL will be measured using the KCCQ, SF-12, and EQ-5D. We will employ two approaches to the analysis of QOL. The first will be to base the analysis on longitudinal mixed effects models. These models would predict outcome from treatment group and time. The mixed modeling approach requires an assumption that patient dropout is ignorable in that the probability of dropping out at any time is related only to previously observed data. Of course, this assumption may not hold, and moreover it is

impossible to test robustly from the data at hand. An alternative approach we will also use, not subject to this criticism, will be to separate the data into strata defined by the time of death or dropout. We will then estimate a separate linear model, including a treatment effect, for the data in each stratum. This method, known as pattern-mixture modeling, is not sensitive to un-testable assumptions about the dropout mechanism because it models the data directly in strata defined by dropout time. The method of Wu and Bailey is an instance of pattern-mixture modeling.

Adverse Events: Differences in the incidence of individual AEs within 24 months post-randomization will be compared between randomization arms using Poisson regression. Ninety-five percent confidence intervals (based on the Poisson distribution) for the risk ratios for individual AEs for treatment with MVS and TV annuloplasty versus MVS alone will be computed.

NYHA classification: The distribution of NYHA at 12 and 24 months will be presented for each randomization arm and compared using a chi-squared test.

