Appendix I: Moderate Tricuspid Regurgitation Trial Echocardiographic Image Acquisition Protocol

General Considerations:

- For the echocardiogram, the patient will be positioned in left lateral recumbency or in the position that permits optimal imaging. All images should be acquired during quiet respiration unless otherwise specified.
- At least 3 and no more than 5 cardiac cycles are requested for two-dimensional imaging unless otherwise specified. At least 5 cardiac cycles are required for spectral pulsed wave (PW) and continuous wave (CW) Doppler. For patients in atrial fibrillation, a minimum of 2 captures of 5 consecutive cardiac cycles are required. Unless otherwise specified, depth should be adjusted to maximize the image while including all necessary structures. Harmonic imaging should be employed to optimize visualization of endocardial borders.
- All PW, CW Doppler and m-mode recordings will be performed at a sweep speed of 100 mm/sec. Gain should be adjusted to reduce excess noise. Color Doppler Nyquist limits will be adjusted to the range of 50-70 cm/sec, unless otherwise specified. The following protocol is required however additional images should be obtained at the discretion of the sonographer/physician.

I. Protocol for Transthoracic Echocardiogram (TTE) pre and post-surgery

1. Parasternal long axis
 - 2D image
 - Color Doppler across aortic and mitral valves
 - Zoom image of LVOT
 - Zoom image of vena contracta
2. Parasternal right ventricular inflow view of the tricuspid valve
 - 2D image include RV and RA (optimize endocardium)
 - Color Doppler across tricuspid valve (TV) including distal jet into RA
 - Zoom view of TV annulus (for measurement of TV annulus)
 - Zoom view of vena contracta proximal jet of TR
 - Zoom view of the proximal flow convergence region of the TR jet after baseline shifted downward (same direction as TR jet flow) to a Nyquist of 25-35 cm/s
 - Continuous wave Doppler across TV valve to estimate TV gradient.
3. Parasternal outflow view of the pulmonic valve
 - 2D
 - Color Doppler across PV

- Pulse wave Doppler
- CW of the pulmonary valve
- Zoom 2D image of pulmonary valve annulus for measurement of the pulmonary annular diameter.

4. Basal PSAX (at the aortic valve level)

- 2D image include TV, short axis of aortic valve and RVOT
- Color Doppler of TV include distal jet into right atrium
- Zoom view of Color Doppler view of vena contracta of TR

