- Zoom view of the proximal flow convergence region of the TR jet after baseline shifted downward (same direction as TR jet flow) to a Nyquist of 25-35 cm/s
- Pulsed Doppler sample of pulmonary flow at the level of the pulmonary valve to measure pulmonary velocity time interval (VTI) opening and closing transients of the pulmonary valve should be recorded.

5. PSAX of ventricles: ensure on-axis views and include right ventricle

- Level of the mitral valve when both anterior and posterior leaflets are visualized.
- Mid-papillary muscle level.
- Level of the apex

6. Apical 4-chamber view

- Full sector to include all four chambers
- Focus on right heart: 2D to Include RV and RA, making sure to include lateral wall of RV (often requires a slight medial tilt of transducer)
- Zoom view of RV only (include base of RV/TV annulus and optimize RV endocardium)
- Color Doppler across TV one including right atrium to capture the distal jet taking care to include wall-impinging eccentric jets in the region of interest.
- Zoom view of TV annulus (for measurement of TV annulus)
- Zoom view of Color Doppler across TV to image the vena contracta of the TR jet
- Zoom view of the proximal flow convergence region of the TR jet after baseline shifted downward (same direction as TR jet flow) to a Nyquist of 25-35 cm/s
- PW of TV at leaflet tips and at level of TV annulus
- CW of TV for estimation of pulmonary artery systolic pressure
- M-mode across lateral tricuspid annulus (for TAPSE measurement)
- Tissue Doppler of lateral tricuspid annulus (to measure peak annular velocity)
- Focus on left heart:

- 2D include both LV and LA
- Zoom view of LV only (avoid foreshortening of LV apex)
- Color Doppler across MV one including left atrium to capture the distal jet taking care to include wall-impinging eccentric jets in the region of interest.
- Zoom view of MV annulus (for measurement of MV annulus)
- -Zoom view of the proximal flow convergence region of the MR jet after baseline shifted downward (same direction as MR jet flow) to a Nyquist of 30-40 cm/s
- PW of MV at leaflet tips and at level of MV annulus
- PW Doppler of right pulmonary vein flow. The sample volume should be placed at least 1 cm within the pulmonary vein
- CW of MV
- Tissue Doppler of lateral and septal mitral annulus

7. Apical 5-Chamber view

- Color flow Doppler across LVOT/Aortic valve

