6.5.2 Analyses of Secondary Clinical Endpoints

6.5.2.1 Clinical and Functional Outcomes

MACCE: The rate of major cerebrovascular or cardiac events (defined as the

composite event of death, stroke, and serious heart failure events) will be compared between randomization groups over 24 months post-randomization using a Cox proportional hazards regression model.

Reoperation for TR: The difference in the rate of requiring subsequent TV annuloplasty after the initial MVS will be compared between randomization groups over 24 months post-randomization. Reoperation for TR may not occur because death from any cause precedes the event; thus, it is possible that censoring patients at all-cause mortality will lead to biased estimates when analyzing time to first event. Therefore, competing risks analysis using the methods of Fine and Gray (Fine & Gray, 1999) will be used to estimate group differences.

NYHA: The distribution of NYHA at 30 days, 6, 12 and 24 months will be presented for each randomization arm and compared using chi-squared tests.

Diuretic Use: The distribution of diuretic use at 30 days, 6, 12 and 24 months will be presented for each randomization arm and compared using chi-squared tests.

Six Minute Walk: Differences between groups in the distances travelled during the 6MWT at 30 days, 6, 12 and 24 months will be compared using Wilcoxon Rank-Sum tests.

Gait Speed Tests: Differences between groups in gait speed at 12 and 24 months will be compared using Wilcoxon Rank-Sum tests.

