6.5.2.2 Echocardiography

Degree of TR: The distribution of the degree of TR at hospital discharge, 12, and 24 months will be presented for each randomization arm and compared using chi-squared tests. Between group differences in TR progression defined as presence of severe TR at 24 months, or for patients enrolled with less than moderate TR, progression by two grades compared to baseline will be compared using a two-tailed 0.05 level chi-squared test.

Additional echo parameters: RV size, RV function (normal, mildly impaired, moderately impaired, severely impaired, peak tricuspid annular velocity, TAPSE, RVFAC), and pulmonary artery pressure at 12 and 24 months will be compared between groups. RV volume as assessed by 3D TTE at 12 and 24 months will be compared between groups. Continuous variables will be compared for between group differences using the Wilcoxon Rank Sum test, and the level of function by chi-square test.

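### Minor: walk distance, gait speed and continuous echo outcomes are compared on follow-up values alone although their baselines are collected; a prespecified baseline-adjusted rank test would be more efficient

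*SAP*

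**What the plan says.** For the six-minute walk, SAP 6.5.2.1 says that differences between groups "in the distances travelled during the 6MWT at 30 days, 6, 12 and 24 months will be compared using Wilcoxon Rank-Sum tests". For gait speed it says "Differences between groups in gait speed at 12 and 24 months will be compared using Wilcoxon Rank-Sum tests". SAP 6.5.2.2 treats peak tricuspid annular velocity, TAPSE, RVFAC, pulmonary artery pressure and 3D RV volume at 12 and 24 months alike: "Continuous variables will be compared for between group differences using the Wilcoxon Rank Sum test". The protocol's Analyses of Secondary Endpoints agrees: "Differences between groups in gait speed and the distances travelled during the 6MWT will be compared using the Wilcoxon Rank-Sum test".

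Baselines exist for all seven outcomes:

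- The Data Collection Schedule marks the walk test, gait speed, 2D TTE and 3D TTE at screening/baseline.
- Definitions and Measurement of Endpoints says "Frailty will be assessed using the Gait Speed Test administered at baseline and reassessed at 12 and 24 months post-randomization".
- The baseline Echocardiogram section adds "In addition, the sites will perform a 3D TTE to assess RV volume".
- Appendix I has a single 2D acquisition protocol, headed "Protocol for Transthoracic Echocardiogram (TTE) pre and post-surgery". It includes the views for TAPSE, annular velocity and pulmonary artery pressure, and its measurement list includes RVFAC.

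Three other provisions bear on the point. SAP 6.1 defines change from baseline but attaches no test to it. SAP 6.2.1 does not impute missing baselines. SAP 6.5.1.4 foresees covariate adjustment only for the primary endpoint, and only after a marked imbalance.

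**The concern.** A patient's preoperative walk distance or TAPSE may predict the later value. If it does, a test that ignores it leaves explainable variation in the error term and has less power than the data allow.

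Right-heart function and functional status are stated secondary aims. The protocol plans the secondary analyses to help interpret a primary endpoint that it expects to be driven largely by echo findings. A real difference in these measures could be missed for want of a covariate already in the database.

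The plan also names no between-arm effect estimate or interval for these outcomes, so a reader would get descriptive summaries and a p-value.

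**Working it through.** The documents state no power, standard deviation, target difference or correlation for these seven outcomes, so there is no planned figure to reproduce. The check compares the planned test with the adjusted one.

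**From the documents:** two-sided 0.05 level (SAP 6.1); 400 patients, 1:1 (SAP 6.5.1.1).

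**Assumed:** correlation r between baseline and follow-up from 0 to 0.7; 180 patients per arm with a follow-up value; 0 to 30% of baselines missing completely at random; a TR stratum holding 40% of patients with no prognostic effect; a shift that gives Wilcoxon about 80% power. That shift is (1.960 + 0.842) × √(2/180) / √(3/π) = 0.302 SD.

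**Formula.** For normal data the rank correlation is r_s = (6/π) × arcsin(r/2). If a fraction f of baselines is observed and the rest carry a missing-baseline indicator, the variance of the adjusted rank test relative to Wilcoxon is v = 1 − f × r_s². Power is Φ(2.802/√v − 1.960), and 400 adjusted patients are worth 400/v unadjusted ones. For r = 0.3 and f = 1: r_s = 0.288, v = 1 − 0.083 = 0.917, power = 83.3%, and 400/0.917 = 436.

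| r | r_s | v (f = 1 / 0.8) | Power (f = 1 / 0.8) | Equivalent N (f = 1 / 0.8) |
|---|---|---|---|---|
| 0 | 0 | 1 / 1 | 80% / 80% | 400 / 400 |
| 0.3 | 0.288 | 0.917 / 0.934 | 83.3% / 82.6% | 436 / 428 |
| 0.5 | 0.483 | 0.767 / 0.814 | 89.2% / 87.4% | 521 / 492 |
| 0.7 | 0.683 | 0.534 / 0.627 | 97.0% / 94.3% | 750 / 638 |

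**Simulation** (4,000 runs per row, bivariate normal), power:

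| r | Baselines missing | Wilcoxon | Rank-ANCOVA, indicator | Rank-ANCOVA, complete-case |
|---|---|---|---|---|
| 0 | 0% | 79.0% | 78.7% | 78.7% |
| 0 | 20% | 80.1% | 80.0% | 70.2% |
| 0.3 | 0% | 79.2% | 82.6% | 82.6% |
| 0.3 | 20% | 80.2% | 82.4% | 74.0% |
| 0.3 | 30% | 79.0% | 81.9% | 67.4% |
| 0.5 | 0% | 80.3% | 89.2% | 89.2% |
| 0.5 | 20% | 79.6% | 87.0% | 80.5% |
| 0.5 | 30% | 80.3% | 86.8% | 75.6% |
| 0.7 | 0% | 79.5% | 96.6% | 96.6% |
| 0.7 | 20% | 79.8% | 93.4% | 92.2% |

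Formula and simulation agree. With the indicator there is no material loss at r = 0.

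**Why the missing-baseline rule matters.** Dropping patients without a baseline multiplies information by (1 − m)/(1 − r_s²), where m is the missing fraction. This falls below 1 once m exceeds r_s², that is 0.083, 0.233 and 0.466 at r = 0.3, 0.5 and 0.7. Complete-case adjustment can therefore do worse than the planned test.

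**Type I error.** The indicator version rejected in 4.9% to 5.4% of null runs. A closely related version (ranks residualised on baseline, 12% of baselines missing) rejected in 4.7% to 5.8%, against 4.8% to 5.4% for Wilcoxon.

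**Skewed data.** With lognormal values, r = 0.3 and 20% of baselines missing, power was 79.0% for Wilcoxon, 82.0% for rank-ANCOVA with the indicator and 62.0% for linear ANCOVA. Coverage of the linear ANCOVA 95% interval was 94.4% to 95.6% over all runs. Linear ANCOVA thus serves as the estimate but not as the test.

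**The case against.** **It is a preference, not an error.** An unadjusted rank test in a randomised comparison is legitimate and simple, and no passages conflict. This stands, and it is why the point is minor.

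**The size is assumed.** No correlation is given, and surgery between the measurements may weaken it. At r = 0.3 with 20% of baselines missing the simulated gain is 82.4 − 80.2 = 2.2 points. This also stands: the direction is secure and the size is not. The larger gains apply only to outcomes that track baseline well.

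**A rank p-value beside a linear interval can disagree.** In lognormal simulations (r = 0.3, 20% missing) the rank test was significant while the linear interval included zero in 22.7% of trials, and the reverse held in 3.6%, about 26% in all. With normal data discordance was 4% to 5%. This is a real cost when data are strongly skewed, and the SAP must say which result governs. A Hodges-Lehmann interval beside Wilcoxon would avoid the mismatch, but would leave the baseline unused.

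**Baseline already has a role.** SAP 6.1 defines change from baseline, and the protocol relates changes in gait speed and walk distance to other outcomes. Neither is a comparison between arms. SAP 6.1 also allows better methods if a planned one proves unsuitable, but Wilcoxon is not unsuitable, so that clause does not prespecify adjustment.

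**Some baselines may be absent.** Gait speed was added in revision 2.0, and the protocol concedes technical limits of 3D echo. The indicator deals with this: baseline precedes randomisation, so its absence cannot depend on the assigned arm.

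**Outcomes missing through death or dropout** are not addressed. True, but the proposal leaves that problem as it finds it.

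**Conclusion.** The concern holds, as a minor point. The planned tests control type I error but leave a collected covariate unused. Relative to a comparison with about 80% power, adjustment adds nothing at a correlation of 0, about 3 points at 0.3, about 9 at 0.5 and about 17 at 0.7 with complete baselines. With 20% of baselines missing and an indicator, the gains are about 2, 7 and 14 points at 0.3, 0.5 and 0.7.

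These figures rest on the assumed correlations, 180 patients per arm, normal data and baselines missing completely at random. The primary analysis, its power and the sample size are unaffected.

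**What to change.** In SAP 6.5.2.1 and 6.5.2.2, prespecify one between-arm test per visit for the seven continuous outcomes: regress the ranked follow-up value on arm, ranked baseline and TR stratum. Keep every patient with a follow-up value by setting a missing baseline rank to the mean rank and adding a missing-baseline indicator. Record that rule in SAP 6.2.1. Retain the unadjusted Wilcoxon test as a sensitivity analysis.

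Alongside the test, report the baseline-adjusted mean difference with its 95% interval from linear ANCOVA, using the same covariates and indicator. State that the rank test supplies the p-value and that the linear model supplies the estimate only.

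The cost is a few sentences and routine code, with no new data. The SAP allows revision before data lock. The downsides are the extra missing-baseline rule and the possible disagreement between p-value and interval when data are skewed.

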6.5.2.2 Echocardiography

Degree of TR: The distribution of the degree of TR at hospital discharge, 12, and 24 months will be presented for each randomization arm and compared using chi-squared tests. Between group differences in TR progression defined as presence of severe TR at 24 months, or for patients enrolled with less than moderate TR, progression by two grades compared to baseline will be compared using a two-tailed 0.05 level chi-squared test.

Additional echo parameters: RV size, RV function (normal, mildly impaired, moderately impaired, severely impaired, peak tricuspid annular velocity, TAPSE, RVFAC), and pulmonary artery pressure at 12 and 24 months will be compared between groups. RV volume as assessed by 3D TTE at 12 and 24 months will be compared between groups. Continuous variables will be compared for between group differences using the Wilcoxon Rank Sum test, and the level of function by chi-square test.

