Appendix III: New York Heart Association Classification (NYHA)

Class	Patient Symptoms
Class I (Asymptomatic)	No limitation of physical activity. Ordinary physical activity does not cause undue fatigue, palpitation, or dyspnea (shortness of breath).
Class II (Mild)	Slight limitation of physical activity. Comfortable at rest, but ordinary physical activity results in fatigue, palpitation, or dyspnea.
Class III (Moderate)	Marked limitation of physical activity. Comfortable at rest, but less than ordinary activity causes fatigue, palpitation, or dyspnea.
Class IV (Severe)	Unable to carry out any physical activity without discomfort. Symptoms of cardiac insufficiency at rest. If any physical activity is undertaken, discomfort is increased.

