5. STUDY ENDPOINTS

5.1 Primary Endpoint

The primary endpoint will be a composite of death, reoperation for TR, or progression of TR from baseline, prior to randomization, by two grades or the presence of severe TR at 2 years post randomization.

Degree of TV regurgitation will be categorized according to American Society of Echocardiography guidelines as none/mild/moderate/severe. Trace regurgitation is also used in the event that regurgitation is barely detected.

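### TR grade, RV function grade and NYHA class are ordered scales, but the planned chi-squared tests ignore the order and no effect estimate is planned

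*SAP*

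**What the plan says.** SAP 6.5.2.2 states its plan for TR grade as follows: "degree of TR at hospital discharge, 12, and 24 months will be presented for each randomization arm and compared using chi-squared tests". For RV function, the same section compares "the level of function by chi-square test". For NYHA, SAP 6.5.2.1 reads: "The distribution of NYHA at 30 days, 6, 12 and 24 months will be presented for each randomization arm and compared using chi-squared tests". The protocol's Analytical Plan also names the chi-squared test for NYHA class (at 12 and 24 months) and for level of RV function.

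All three scales are ordered. TR is "categorized according to American Society of Echocardiography guidelines as none/mild/moderate/severe" (SAP 5.1), and Protocol Appendix I merges none and trace, which leaves four grades. Appendix I lists RV function from normal to severely impaired in four steps, and Appendix III lists NYHA classes I to IV.

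The plan has a rank method but keeps it for other measures: "Continuous variables will be compared for between group differences using the Wilcoxon Rank Sum test". The six-minute walk and gait speed also get it. SAP 6.5.2.2 adds a separate two-sided chi-squared test of TR progression as a yes/no outcome (severe TR at 24 months or, for those enrolled with less than moderate TR, worsening by two grades).

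**The concern.** A general chi-squared test on a 2 × 4 table has 3 degrees of freedom and gives the same p-value if the four grades are relabelled in any order. It tests whether the arms differ in some way, not whether one arm sits lower on the scale, and it gives no estimate. By contrast, the plan analyses MACCE and mortality with Cox models and adverse events with rate ratios and 95% intervals. The primary endpoint itself relies on the order of the TR grades, because it counts two-grade worsening.

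Two things are at stake. If annuloplasty shifts patients across the grades, the planned test is less likely to detect it than an ordinal test on the same data. And whatever the p-value, the report would contain no effect size with an interval for these endpoints.

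**Working it through.** **The plan's own figure.** The only power statements are for the primary endpoint and MACCE; there is none for the graded endpoints. The design figure (SAP 6.5.1.1) is 200 per arm, 25% versus 12%, two-sided 0.05:

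- pooled proportion 0.185; SE under the null √(2 × 0.185 × 0.815 / 200) = 0.0388
- SE under the alternative √((0.25 × 0.75 + 0.12 × 0.88) / 200) = 0.0383
- power = Φ((0.13 − 1.96 × 0.0388) / 0.0383) = Φ(1.41) = 92%

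Power is 91.9% at the final critical value of 1.969, and 88.4% with 3% crossover in both arms. The stated figure of about 90% therefore reproduces.

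**Cost of the extra degrees of freedom.** If the whole effect lies along the ordered scale, a 1-df test with 80% power has noncentrality 7.85. A 3-df test with that noncentrality has 64% power. It needs 10.90 to reach 80%, so 10.90 / 7.85 = 1.39 times the patients. At 90% power the figures are 10.51 and 14.17: a ratio of 1.35, and 78% power for the 3-df test.

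**Simulation under a proportional shift.** The documents give no grade distributions, so these inputs are assumptions:

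- 190 evaluable patients per arm (95% of 200)
- control distributions of 30/40/22/8% for TR, 50/30/15/5% for RV function and 55/33/10/2% for NYHA
- treated distribution: each cumulative odds multiplied by a common odds ratio. For TR at 1.7, cumulative odds of 0.429, 2.333 and 11.5 become 0.729, 3.967 and 19.55, which gives 42.1/37.7/15.3/4.9%.

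The tests are Pearson chi-squared and the tie-corrected, unstratified Wilcoxon rank-sum, with 100,000 simulated trials per setting. Power in % (chi-squared, then rank-sum):

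| Odds ratio | TR grade | RV function | NYHA | Gain, points |
|---|---|---|---|---|
| 1.5 | 41, 57 | 37, 54 | 35, 51 | 16 to 17 |
| 1.7 | 64, 80 | 59, 76 | 56, 73 | 16 to 17 |
| 2.0 | 88, 95 | 83, 93 | 80, 91 | 8 to 11 |
| 2.44 | 98, 99.7 | 97, 99 | 95, 99 | 1 to 4 |

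Gains were taken before rounding. Type I error is about 5% for both tests. The last row uses the odds ratio implied by the primary endpoint, (0.25/0.75) / (0.12/0.88) = 2.44. That figure belongs to the composite, not to any graded scale.

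**Simulation without proportionality.** TR control 30/40/22/8%, 190 per arm:

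| Treated distribution | Chi-squared | Rank-sum |
|---|---|---|
| 30/50/18/2% | 77% | 30% |
| 30/47/22/1% | 87% | 21% |
| 35/47/16/2% | 80% | 63% |
| 40/44/14/2% | 89% | 89% |

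When the change is confined to the top grades, chi-squared is clearly better.

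**Does the binary TR test cover that case?** Take severe TR alone, 8% versus 2%, 190 per arm. The pooled proportion is 0.05, the null SE 0.0224 and the alternative SE 0.0221. Power is Φ((0.06 − 1.96 × 0.0224) / 0.0221) ≈ 77% (80% by simulation). The planned binary outcome also counts two-grade worsening, so this is only a guide, but a binary test on severe TR recovers what the rank test loses.

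**The case against.** The strongest objection is that the gain depends on the pattern of effect. Annuloplasty is meant to prevent progression to the upper grades, and for an effect of that shape the rank-sum test can lose most of its power. This stands. A reader might infer that the planned tests generally miss effects that an ordinal test would find, but that is true only for roughly proportional shifts. For TR at 24 months the binary progression test largely covers the exception. For TR at discharge and 12 months, RV function and NYHA there is no such backup.

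Second, the gap is widest at modest odds ratios and nearly gone at 2.44. This also stands. The documents fix no effect size for these scales, so neither range can be preferred.

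Third, direction can be read from the distributions that SAP 6.5.2.1 and 6.5.2.2 require for TR and NYHA, and RV function is also compared on TAPSE, RVFAC and annular velocity by rank-sum. That is so, but the tables give no estimate or interval. The rank-sum test gives none either; only the added model does, and it brings an assumption.

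Fourth, a 1-df trend form of chi-squared may be intended. Nothing says so, and diuretic use and 30-day vital status get the same wording. If it is intended, the text should name it.

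Fifth, SAP 6.1 lets unsuitable methods be replaced during analysis. That clause does not help, because the chi-squared test is not unsuitable, and a test chosen after seeing the data is what pre-specification is meant to prevent.

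**Conclusion.** The concern holds as an efficiency and reporting weakness in secondary endpoints. For these graded scales the plan ignores the order and promises no effect estimate. Under the assumed distributions, an ordinal test has about 8 to 17 points more power for a proportional shift with odds ratio 1.5 to 2.0 and 1 to 4 points more at 2.44. It has less power when only the top grades change. The simulated rank-sum test was unstratified; a stratified version may differ somewhat.

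The documents do not support several stronger readings. The chi-squared tests are not invalid, since their type I error is about 5%. The primary analysis and the sample size are unaffected. The secondary endpoints are listed without ranking, and the protocol singles out MACCE as the one of special interest, so these scales cannot be called the main secondary endpoints. For RV function, the point covers only the graded level. For RV size, SAP 6.5.2.2 names no categorical test at all, so the gap there is a missing specification.

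**What to change.** In SAP 6.5.2.1 and 6.5.2.2, and in the protocol's Analytical Plan paragraphs on NYHA and additional echo parameters, so that the two documents agree:

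- Compare TR grade, level of RV function and NYHA class at each planned visit with an ordinal test stratified by the baseline TR stratum: van Elteren, or a Cochran-Mantel-Haenszel row-mean-score test with its scores stated.
- Report a common odds ratio with 95% CI from a proportional-odds model that includes the TR stratum, after checking proportionality.
- Specify the same ordinal test for RV size category, which Protocol Appendix I defines as three ordered levels.
- Keep the frequency tables, the binary TR-progression chi-squared test, and chi-squared for yes/no outcomes such as diuretic use.

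This is a cheap improvement: text in two documents, with no new data, visits or patients. The SAP allows revision before data lock. The price is lower power for changes confined to the top grades, which the binary test offsets only for TR at 24 months, and a proportional-odds assumption behind the estimate.
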